7.1 Data post-surgery will not be used for primary analysis - Primary Endpoint

Part A, B and C pooled for weeks 1 to 4 (referred as 'Part A*' hereafter)

The tumor size (volume) as assessed by MRI technique up to and including week 4 will be the primary measure of efficacy. This data will be listed as collected.

Consolidated tumor volume will be calculated as the geometric mean from two readers. Summary statistics of the consolidated tumor volume will be presented by treatment and visit time. The tumor volume measured at screening is treated as baseline. The percent change and absolute change from baseline of the consolidated tumor volume will be summarized in the same fashion. Waterfall plot on percent change from baseline after 4 weeks will be produced. The tumor size at baseline and after 4 weeks will be log transformed. The log ratio to baseline of the tumor size (change from baseline of log transformed volume) will be the primary measure of efficacy for the single dosing part of the study (Part A*).

The analysis of the primary endpoint will quantify the accumulation of evidence about the treatment effect as patients complete their 4 week treatment. The evidence will be summarized in the posterior distributions of the treatment group means and their differences. These posterior distributions will be updated after certain patients complete the 4 week treatment.

For the analysis, the distributional model for the observed data (log ratio) will be the normal model with unknown parameters μ and σ , with μ being the parameter of primary interest (treatment mean) and σ representing the sampling error. This model will be applied to each MCS110 dose group separately. Little prior information is available for these parameters and therefore non-informative prior distributions will be placed on them. For μ a normal prior distribution centered at 0 (no treatment effect) will be used with large standard deviation, and for σ a uniform (0,2) prior distribution.

The model is formally described below, LR being the log ratio of tumor volume:

Likelihood

$$LR_i \sim N(\mu, \sigma)$$

with

$$\mu = \mu_p \text{ for observations from placebo group}$$

$$\mu = \mu_m \text{ for observations from MCS110 group}$$

Prior distributions on treatment means μ 's

$$\mu_p \sim N(0, 0.3)$$

$$\mu_m \sim N(0, 10) \text{ * i.e. Neutral prior or}$$

$$\mu_m \sim N(0, 0.3) \text{ * i.e. Skeptical prior}$$

Prior distributions on sigma

$$\sigma \sim \text{Uniform}(0,2)$$

Decision Rule

The PoC criterion is two-fold, as follows:

- $\text{Prob}(LR(\text{treated}) < LR(\text{placebo})) > 0.90$; i.e. 90% confidence in superiority to placebo
- $\text{Prob}(LR(\text{treated}) - LR(\text{placebo}) < \log(0.6)) > 0.50$; i.e. 50% confidence in the treated group ratio being 40% below the placebo group ratio

[figure not shown]
At least one placebo patient and two MCS110 patients must be included to declare PoC. Both neutral and skeptical priors will be used to assess the PoC criterion. The skeptical prior is used to shift prior beliefs toward no effect of MCS110 i.e. stronger evidence from the data in favor of MCS110 will be needed to reach PoC. The skeptical analysis will only be run as a sensitivity analysis.

Once the PoC criterion is reached, the clinical trial team (CTT) may decide to continue recruitment to collect more data on MCS110.

If after 6 patients have completed the 4 week treatment, the PoC criterion is not reached, the probability to reach PoC with the addition of 6 new patients will be assessed, and if this probability is less than 10% the trial may be stopped for futility.

For illustration, an example of a trial path simulation with skeptical and neutral priors on mean treatment effect in MCS110 group is shown below ([Figure 7-1](#)):

Figure 7-1 Example of a sample path

The left plot displays the skeptical analysis and the right plot the neutral analysis.

The blue dots represent the posterior mean in the MCS110 group and the black dots represent the posterior means in the placebo group as more patients contribute data.

The green dots show the probability of MCS110 being superior to placebo, and the pink dot the probability to be better by 40%.

In this example, the PoC criterion is reached after 3 patients when neutral prior (second graph) is used, and after 4 patients when skeptical prior (first graph) is used.

The posterior probability of LR(treated), LR(placebo) and their difference will be estimated using MCMC techniques using at least 40000 simulations discarding a sufficient number of the initial samples to insure convergence of the markov chain (based on trace plot visual inspections).

In the event that there are any complete responders a square root ratio analysis will be performed instead. In this analysis everything else will be the same as above other than using square root ratio instead of log ratios.

The same model as above will also be applied to compare the efficacy of the 3 mg/kg and 5 mg/kg to the 10 mg/kg dose (instead of Placebo).

Part B and C (referenced as Part B* hereafter)

Part B includes all data from multiple dosing Parts. In Part B, treatment group 1 = MCS110 throughout the trial, treatment group 2 = Placebo for the first dose and MCS110 from the second dose. In Part C, treatment arm 1 = MCS110 3 mg/kg, treatment arm 2 = MCS110 5 mg/kg, treatment arm 3 = MCS110 10 mg/kg, for patients in treatment arms 1 and 2 that switch to 10 mg/kg after 3 doses, they will be included in their original treatment group for the first 3 doses and will added in a separate group after that (4= MCS110 3 mg/kg for 3 doses and 10 mg/kg afterwards and 5= MCS110 5 mg/kg for 3 doses and 10 mg/kg afterwards), no re-calculation of baseline will occur for the people who change treatments.

Tumor volumes will be listed at each MRI assessment timepoint till the end of the study by treatment groups.

Part B*: MCS110 data only, by including data starting from the 1st dose of MCS110 in all treatment groups of Parts B and C. More specifically, for Part B treatment group 2, the measurement right before patients receiving the first dose of MCS110 (2nd dose from screening) will be treated as the new baseline and assessment time-points will be adjusted accordingly. Summary statistics of the consolidated tumor volume for the raw values, percent change and absolute change from baseline.

Arithmetic mean (+/-) SE on percent change from baseline vs time plot will be produced for Part B*. Waterfall plot of the maximum reduction until 8 Weeks after last dose will be produced in regards of number of doses received.

Overall Time to complete tumor ablation will be summarised up to the primary endpoint (8 weeks after the last MCS110 dose), along with a summary of overall time to $\geq 50\%$, and $\geq 80\%$ ablation. The number and frequency of patients reaching each level will also be included in the summary.

Overall Time to complete ablation is the time (in weeks) - from first MCS110 dose to the first time when there is no tumor detected. Overall time to $\geq 50\%$, and $\geq 80\%$ ablation is the time from first MCS110 dose to reach maximum ablation of [50%, 80%) and [80%, complete) respectively.

Part C

Tumor volumes will be listed and descriptively summarized at each MRI assessment time by treatment arm (treatment arm 1 = MCS110 3 mg/kg, treatment arm 2 = MCS110 5 mg/kg, treatment arm 3 = MCS110 10 mg/kg). For patients in treatment arms 1 and 2 that switch to 10 mg/kg after 3 doses, they will be treated as a separate group throughout the study (4= MCS110 3 mg/kg for 3 doses and 10 mg/kg afterwards and 5= MCS110 5 mg/kg for 3 doses and 10 mg/kg afterwards) This approach will be applied for all analyses of Part C where the treatment group is used. In addition, incidences of patients with partial response (PR), stable disease (SD) and progressive disease (PD) will be listed by treatment arm.

All summary tables (tumor volumes and response) will also be provided by age group (<18 years and ≥ 18 years).

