3.4 Rationale for choice of comparator

In Part A and first dose Part B, placebo is used as a comparator to obtain confirmation that during the natural course of the disease the tumor volume changes are very small in 4 weeks. It also allows to estimate or calculate the variability of the tumor volume analysis method by MRI, as this method has not been used or reported before for the quantitative measurement of PVNS tumors.

In Part B, the first dose will be compared to placebo (in a 2 MCS110:1placebo ratio) to continue to increase confidence in the original result from Part A, and to increase experience with change in PVNS tumor volume by MRI over a 4-week period. Repeat MRI measures of PVNS tumor volume have not been published in the literature. Patients who are assigned to placebo arm for the first dose in Part B will receive active drug MCS110 4 weeks later, then every 4 weeks up to a total of 6 doses.

Sufficient data on placebo were collected in Part A and B to get an estimation of the variability of the MRI assessment of tumor volume reduction. In Part C no placebo will be administered.

There will not be any active comparator, as there is no approved drug available today to treat PVNS.

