6.4 Efficacy / Pharmacodynamic assessments

6.4.1 Tumor Volume by MRI

Collection and processing

MRI of the joints with PVNS will be taken during the screening phase. MRI scans have to be scheduled so, that a validated reference MRI should be available within 8 days before patient dosing (Part A and B).

For Part C, a validated reference MRI should be available within 3 weeks before patient randomization. This will allow for the evaluation of the image quality and measurability of tumor sizes. For screening and follow up MRI radiologists should schedule two appointments with the patient with a window of two days to account for a potential rescan.

If this MRI is not validated, a second MRI should be planned to get a validated reference MRI during screening period.

At visits including treatment administration, MRI should be scheduled within 5 days before MCS110 dosing day.

In Part C, at week 12, dose decision point, the MRI should be planned in a sufficient time before dosing day (at least 5 working days) to allow tumor volume evaluation and decision making on potential dose escalation.

Confidential

All MRI scans will be transferred to the Imaging CRO (ICRO) electronically to determine if the images are of good quality without artifacts and to be reviewed by a central radiologist to confirm that the patient has at least one target lesion of measurable tumor size at screening, with minimum lesion dimension of at least 4 times the slice thickness and no less than 10 mm in the longest axis. If the images are not of good quality and/or not measurable, the ICRO will inform Novartis and the clinical sites within 48 hours and will request a new scan. If acceptable, the ICRO will also inform Novartis and the clinical sites and this will be considered as the validated reference MRI. The MRI image is read by two independent readers, for all scans at all timepoints. The RECIST value for the Overall Best Response is taken as the value provided by the first reader. If the values between two readers do not match for overall best response this should be queried by data management and the readers should meet to reach consensus. In addition readers should meet to reach consensus if there is discrepancy in the number of lesions observed.

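### SAP 7.1 sets 3 and 5 mg/kg against placebo patients from other study parts at week 4, so a lower-dose claim under the proof-of-concept rule would be non-randomised

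*SAP*

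**What the plan says.** SAP 7.1 defines a week-4 data set, Part A*, as "Part A, B and C pooled for weeks 1 to 4", and makes the log ratio of tumor volume to baseline the primary measure for it. The model has one mean "for observations from placebo group", one mean for MCS110 and one common sigma. On dose it says: "This model will be applied to each MCS110 dose group separately". No term for study part appears. The two-part PoC rule against placebo follows directly. SAP 7.1 then adds a comparison of 3 and 5 mg/kg with 10 mg/kg, described as replacing placebo, which implies that the first comparison of those doses is with placebo.

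SAP 7.1.2 counts 5 placebo patients: 2 in Part A and 3 at the first dose of Part B. Protocol 3.4 states: "In Part C no placebo will be administered".

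Protocol 9.4.2 gives this model and rule under Part A only and treats Parts B and C descriptively. Protocol 9.5 pools the first 4 weeks of all parts, but for secondary variables.

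**The concern.** The PoC rule was built for a randomised contrast. For 3 and 5 mg/kg the contrast with placebo is dose plus every difference between Part C and Parts A and B, and the documents show several:

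- Part A took PVNS patients expected to have surgery, with at most two operations on the joint. Part B added GCTTS. Part C added patients from age 12 (Protocol 4.1 and 4.2).
- Protocol 6.4.1 asks for the reference scan within 8 days of dosing in Parts A and B, but "For Part C, a validated reference MRI should be available within 3 weeks before patient randomization". SAP 7.1 takes the screening volume as baseline.
- SAP 7.1.2 notes that the placebo group may have shown a response that changes over time. It allows for this in the supportive dose-time-response model, but not in the model that carries the PoC rule.

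Identifying a dose below 10 mg/kg with the same efficacy is the stated goal of Part C (Protocol 3.2.3.2). A lower dose reported as meeting, or missing, a superiority criterion would bear on that goal.

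**Working it through.** **1. Who is in the week-4 pool.** Part A treated 7 patients (Protocol 3.2.1), 2 on placebo, so 5 on MCS110. Part B had 11 patients (Protocol introduction), 3 on placebo at first dose, so 8 on MCS110. Part C is planned as about 6/6/3 (Protocol Table 5-1).

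| Part | Placebo | 3 mg/kg | 5 mg/kg | 10 mg/kg |
|---|---|---|---|---|
| A | 2 | 0 | 0 | 5 |
| B | 3 | 0 | 0 | 8 |
| C | 0 | 6 | 6 | 3 |

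The first-dose 10 mg/kg total is 5 + 8 + 3 = 16. The 19 in SAP 7.1.2 appears to add the 3 Part B placebo patients after they crossed over.

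**2. The plan's own figure.** The model has a normal log ratio, "for σ a uniform (0,2) prior distribution", placebo mean N(0, SD 0.3) and MCS110 mean N(0, SD 10), with 2:1 allocation and a true ratio of 0.5. Simulated at a single look, it gives 94.8/88.6/81.5% for Scenarios 1/2/3 with 12 patients; Protocol Table 9-1 states 95/89/82%. With 6 patients it gives 87.5/83.1/73.4%, against 88/83/74%. The model and the reading of 0.3 and 10 as SDs are therefore right.

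**3. A lower dose against placebo.** Take 6 versus 5 patients and the protocol's SD of 0.2 x sqrt(2) = 0.283. The between-part shifts in log ratio are assumptions; the documents give none. Chance of meeting PoC, 8,000 trials per cell:

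| True reduction | shift -0.10 | -0.05 | 0 | +0.05 | +0.10 |
|---|---|---|---|---|---|
| none | 0.4% | 0.1% | <0.1% | <0.1% | <0.1% |
| 30% | 37% | 25% | 16% | 9% | 5% |
| 40% | 73% | 62% | 50% | 38% | 25% |
| 50% | 97% | 93% | 88% | 80% | 69% |

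A hand check on the 40% criterion alone: SE = 0.283 x sqrt(1/6 + 1/5) = 0.171, and the chance is about Phi[(log 0.6 - log r - shift)/SE], with r the true ratio.

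- r = 0.7: (-0.511 + 0.357)/0.171 = -0.90, or 18%. With shift -0.10: -0.054/0.171 = -0.32, or 38%.
- r = 0.5: 0.182/0.171 = 1.06, or 86%. With shift +0.05: 0.132/0.171 = 0.77, or 78%.

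**4. Size of the MRI-window effect.** The windows differ by at most 21 - 8 = 13 days. At the protocol's upper bound of 10% growth per 4 weeks, the shift is log(1.10) x 13/28 = 0.044, about +0.05 at most. Its sign is against the drug.

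**5. Would a part term solve it?** Not in the separate fits. With one lower dose and placebo plus part terms, the Part C indicator equals the dose indicator (design rank 3 of 4), so the contrast is not estimable. A joint model can bridge through 10 mg/kg. The Parts A and B contrast of 10 mg/kg with placebo has variance 1/[1/(1/5 + 1/2) + 1/(1/8 + 1/3)] = 0.277 sigma². Adding 1/6 + 1/3 gives 0.777 sigma², against 1/6 + 1/5 = 0.367 sigma² without part terms. At SD 0.283 the SE goes from 0.171 to 0.249.

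**6. The 10 mg/kg contrast.** Three of 16 patients come from Part C. A 0.05 shift in them moves the arm mean by 0.05 x 3/16 = 0.009. At a true ratio of 0.5 the chance of PoC goes from about 93% to 91%, and it is about 92% if Part C is left out.

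**The case against.** Much of the case on the other side stands.

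- **No stated dose decision uses the pooled PoC result.** Continuing a dose and extending an arm depend on the 45% volume reduction at week 12 (SAP 2.4). Part C's primary outcome is tumor volume 8 weeks after the last dose. The only stated consequences of PoC are optional further recruitment and a futility look at 6 patients.
- **A reader might infer that the lower doses get no randomised comparison.** That is not so. SAP 7.1.2 has a Part C-only week-4 ANCOVA with differences between arms, though worded as optional. SAP 7.1 also compares 3 and 5 with 10 mg/kg, although that comparison follows the pooled set and so appears to mix in 10 mg/kg patients from Parts A and B.
- **A reader might infer that the earlier baseline scan favours the drug.** Growth before dosing does the opposite. The growth figure is an upper bound, and Protocol 3.2.3.1 reports a change of -2% in its one placebo patient at that point. The Part B schedule also counts its 8 days from receipt of MRI validation, so the gap between parts may be smaller than 13 days.
- **The 40% row in the working lies on the threshold of criterion 2**, where sensitivity is greatest by construction. It should not be read alone.
- **Population differences are documented, but an effect on week-4 volume is not.** The protocol expects adolescent tumor tissue to be no different, and Part C eligibility is described as similar to Part B.

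None of this makes lower dose versus placebo a randomised contrast, and Protocol 9.5 does not authorise the pool for the primary rule.

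**Conclusion.** The concern holds as one of interpretation. As written, SAP 7.1 lets a lower dose be described as superior to placebo with 90% confidence on a comparison that has no randomised core. This rests on reading the rule as applying per dose, which follows from the order of the text but is not stated.

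The exposure is a partly active dose: an assumed shift of 0.10 in the drug's favour takes a true 30% reduction from about 16% to 37%. In the other direction, +0.05 lowers the chance from about 88% to 80% at the protocol's planning effect.

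Two stronger readings are not supported. Shifts within 0.10 do not create false PoC when the drug does nothing (at most 0.4%); assumed spurious drops of 20% and 30% would be needed to reach 3.2% and 16.2% at SD 0.283. The 10 mg/kg contrast is not materially damaged, since a randomised comparison remains in Parts A and B and the Part C patients barely move it.

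The figures assume 6 versus 5 patients, SD 0.283 and hypothetical shifts. An arm extended to about 10 would include open-label patients who were not randomised at all.

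**What to change.** In SAP 7.1:

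1. Apply the PoC rule only to 10 mg/kg versus placebo in Parts A and B, where both were randomised, stratified by part. Keep the three-part pool as a sensitivity analysis.
2. Report 3 and 5 mg/kg versus placebo as non-randomised external-control estimates with intervals, and do not apply the PoC rule to them.
3. In SAP 7.1.2, make the Part C-only week-4 dose ANCOVA definite instead of optional. Show it beside the pooled comparison of 3 and 5 with 10 mg/kg, and identify the open-label extension patients.

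The cost is SAP wording and one stratification term, with no new data. The PoC contrast loses about three 10 mg/kg patients (13 versus 5 instead of 16 versus 5), which is negligible. The Part C-only contrast is imprecise: with 6 versus 3 patients the SE is 0.283 x sqrt(1/6 + 1/3) = 0.200, so a 95% interval spans a factor of about exp(1.96 x 0.200) = 1.48 either way. The report should state that limit.

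### With any complete responder, the week-4 PoC rule moves to an undefined square-root ratio but keeps the log-scale priors and log(0.6), so criterion 2 no longer means a 40% reduction

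*SAP*

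**What the plan says.** SAP 7.1 analyses the first four weeks of Parts A, B and C together. The endpoint is the log ratio, the difference between log volume at week 4 and log volume at baseline. The treatment mean gets "a normal prior distribution centered at 0 (no treatment effect) will be used with large standard deviation". In detail, the placebo mean and the skeptical MCS110 mean have N(0, 0.3), the neutral MCS110 mean has N(0, 10), and sigma is Uniform(0, 2).

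PoC needs posterior probability above 0.90 that treated is below placebo. It also needs probability above 0.50 that the difference is below log(0.6), explained as "50% confidence in the treated group ratio being 40% below the placebo group ratio". The skeptical prior is a sensitivity analysis, included so that "stronger evidence from the data in favor of MCS110 will be needed to reach PoC".

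A log of zero does not exist, so the Decision Rule adds: "In the event that there are any complete responders a square root ratio analysis will be performed instead". It continues: "In this analysis everything else will be the same as above other than using square root ratio instead of log ratios".

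On dose groups, SAP 7.1 states: "This model will be applied to each MCS110 dose group separately". It then reuses the model with 10 mg/kg as the reference: "The same model as above will also be applied to compare the efficacy of the 3 mg/kg and 5 mg/kg". Neither document defines the square-root ratio or gives priors or a threshold for it. Protocol 9.4.2 has no square-root rule.

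**The concern.** Zero means no change, and log(0.6) means 40% below placebo, only when the endpoint is a log ratio. Carried unchanged to another scale, these numbers mean something else, and what they mean depends on a definition that the SAP does not give.

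On the most literal reading, one complete response, the best possible outcome, would turn a likely PoC into an almost certain failure. The skeptical prior would also work against its stated purpose, by favouring MCS110. If the gap is left open, the scale, the priors and the threshold would be settled only once a responder is known.

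**Working it through.** **Inputs**
- Decision rule and priors: SAP 7.1. The 0.3 and 10 are read as SDs, and sigma is common to both groups.
- SD of the log ratio: Protocol 9.13, 0.2 x sqrt(2) = 0.283 and 0.3 x sqrt(2) = 0.424. Paired results below are in this order.
- Placebo: 5 patients (2 in Part A, 3 in Part B; SAP 7.1.2), assumed unchanged.
- Active at 10 mg/kg: Part A 7 - 2 = 5, Part B 11 - 3 = 8, Part C 3 (Protocol Table 5-1), total 16. A 3 or 5 mg/kg group has 6.
- Assumption: the complete responder enters with volume 0, since the SAP gives no value.

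**1. Log-scale rule against the plan's own figures.** The same model, at a single fixed look with the neutral prior, gives power for Scenarios 1 / 2 / 3 as follows.

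| N | Protocol Table 9-1 | Recomputed |
|---|---|---|
| 12 | 95 / 89 / 82% | 94.2 / 88.4 / 82.2% |
| 9 | 90 / 85 / 79% | 91.6 / 85.8 / 79.8% |
| 6 | 88 / 83 / 74% | 88.4 / 82.3 / 73.5% |
| 3 | 69 / 62 / 46% | 65.8 / 61.2 / 47.3% |

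Eleven of 12 cells agree within 2 points. The exception is N = 3 in Scenario 1, about 2 Monte Carlo standard errors of the plan's 800-trial run.

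**2. Reading 1: sqrt(V4/V0).** No change is 1 and disappearance is 0. With placebo at 1, criterion 2 needs a treated value below 1 - 0.511 = 0.489. As a volume ratio that is 0.489^2 = 0.239, a 76% reduction. A 40% reduction would be sqrt(0.6) - 1 = -0.225. The N(0, 0.3) priors are centred on disappearance, with no change 1 / 0.3 = 3.3 prior SDs away.

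**3. Reading 2: sqrt(V4) - sqrt(V0).** Zero is again no change, but the threshold depends on the unit. For an assumed 10 mL baseline, the same 40% fall is sqrt(10) x (-0.225) = -0.71 in mL and sqrt(10,000) x (-0.225) = -22.5 in mm3.

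**4. Reading 3: log(0.6) also swapped for sqrt(0.6) = +0.775.** The bound on the difference is positive. Criterion 2 is met in 100% of simulated trials even when the other 15 active patients do not change.

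**5. Simulated PoC rates on reading 1.** Grid posterior, 6,000 trials per cell, one active patient at zero. The true reduction applies to the other active patients. The re-scaled rule is the one under the fix, with prior SD 0.15.

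| 16 active, true reduction | As written, neutral | As written, skeptical | Re-scaled |
|---|---|---|---|
| 0% | not run | not run | 0.0 / 0.5% |
| 20% | not run | not run | 6 / 13% |
| 50% | 0.0 / 0.2% | not run | 99.5 / 96% |
| 70% | 11 / 14% | 14 / 17% | 100 / 100% |
| 80% | 69 / 54% | 72 / 58% | not run |
| 85% | 94 / 82% | not run | not run |

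For comparison, the log rule at 50% with no complete responder gives 92 / 86%. The skeptical prior declares PoC more often than the neutral one.

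**6. Six active patients.** As written: 0.0 / 0.1% at 50% and 10 / 9% at 70%, with the skeptical prior at 26 / 22% at 70%. Re-scaled: 100 / 98% at 50%. One zero weighs heavily here: the re-scaled rule still declares PoC in 13 / 15% of trials when the other five do not change, and in 66 / 52% when they shrink 20%. The log rule without that patient gives 0.1 / 1.2% and 4 / 11%. The arithmetic for the 20% case: mean (5 x sqrt(0.8) + 0) / 6 = 0.745, squared 0.556, an implied 44% reduction.

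**The case against.** **The consequence is small.** The Protocol synopsis reports single-dose reductions of 29-50%, so a complete response at week 4 is unlikely. Part A is already described as positive and Part C was under way. The rule says only that the team may continue or may stop. Reading 1 errs towards not declaring PoC. All of this stands and limits the weight of the point. It does not make the clause right, because it was written for exactly this event and fails when used.

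**A sensible analyst would keep the meanings, not the numbers.** That would lead to priors at no change and a 40% margin. It is the right repair, but the text carries everything over and re-scales nothing.

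**The headline rates belong to reading 1.** True. Reading 2 is the closer analogue of the log definition, has no centring problem, and can be lenient at larger baseline values. So even the direction of the error is unknown until the ratio is defined.

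**The simulated case is artificial.** A zero beside patients clustered near 50% is hardly compatible with the planning SDs, and reductions of 70-85% exceed those reported. The rates show how the rule behaves; they are not forecasts.

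**The re-scaled rule is more lenient than the log rule.** It is. With the others at a 30% reduction, a separate run (2,000 trials per cell) gave 39 / 39% against 12 / 19% on the log scale without the responder for 16 active, and 91 / 74% against 17 / 24% for six. Part of this is a genuine responder being counted. It is why both results should be reported.

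**The reference prior in the dose comparison is not new.** The 10 mg/kg mean inherits N(0, 0.3) on the log scale too. What the switch adds on reading 1 is that the centre moves from no change to disappearance.

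**Conclusion.** The concern holds: the clause is wrong as written, with limited reach, and should be fixed. The transform is undefined, and none of the three readings keeps criterion 2 at 40% once the log-scale numbers are carried over. On sqrt(V4/V0) with placebo unchanged, the required reduction is 76%. At a true 50% reduction with 16 active patients, the PoC rate drops from 92 / 86% to 0.0 / 0.2% when one patient responds completely.

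These rates rest on volume 0 for the responder, five unchanged placebo patients, the planning SDs, and 0.3 read as an SD. Reading 0.3 as a variance would soften the prior problem but not the threshold problem. The Part B and C outcome eight weeks after the last dose is not affected.

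**What to change.** Add one short paragraph to SAP 7.1:
- Define the square-root ratio as sqrt(V4/V0) at week 4, with V4 = 0 for a complete responder.
- Centre the placebo prior and the skeptical MCS110 prior at 1, with a re-scaled SD. The delta method gives 0.5 x 0.3 = 0.15. This value is an assumption; 0.30 changes the 50% result with 16 active only from 99.5 / 96% to 99 / 94%. The neutral N(0, 10) prior can stay.
- Keep criterion 1. Replace criterion 2 by P(mean_treated < sqrt(0.6) x mean_placebo) > 0.50.
- Report the result with and without the complete responder, above all in groups of six.
- For 3 and 5 against 10 mg/kg, carry over only the prior centring.
- Optionally, state that the trigger is a complete response in the week-4 data, since the present wording does not limit it.

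The cost is this paragraph, matching MCMC inputs and one sensitivity run. SAP 1.2 counts a change of statistical model as minor, so a note to file or RAP addendum should be enough. If the sponsor regards a changed decision criterion as major, it needs a new RAP version instead. Either way it should be done before database lock.
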